6.3 Modification in Dose or Schedule for Treatment Response

Once AML patients achieve morphologic complete remission with incomplete blood count recovery (CRi) or MDS patients achieve a marrow complete response (Marrow CR) as defined in Section 9.0, decitabine administration may be decreased to 20 mg/m²/day for ten consecutive days, and the cycles may be administered every 6 weeks to limit myelosuppressive toxicity, at the discretion of the treating physician. After two cycles at six week intervals, the dose may be reduced to 20 mg/m²/day for five consecutive days of treatment in six week intervals. If the patient meets the definition of CR with complete cytogenetic response as defined in Section 9.0, administration may further be decreased to three consecutive days per cycle at the discretion of the treating physician.

[Redacted]

[Redacted]

[Redacted]

[Redacted]

[Redacted]

[Redacted]

[Redacted]

[Redacted]

[Redacted]

[Redacted]

[Redacted]

[REDACTED]

[REDACTED]

[REDACTED]

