9.1 Response Criteria - AML

AML Patients will be assessed for response according to the IWG criteria:¹

Morphologic complete remission (CR) – Defined as morphologic leukemia-free state, defined as less than 5% blasts in aspirate with marrow spicules and a count of ≥ 200 nucleated cells and no blasts with Auer rods or any persistence of extramedullary disease. When erythroid precursors constitute less than 50% of bone marrow nucleated cells, the percentage of blasts is based on all nucleated cells; when there are 50% or more erythroid cells, the percentage blasts should be based on the nonerythroid cells. The presence of mild megaloblastoid changes may be permitted if they are thought to be consistent with treatment effect. However, persistence of pretreatment abnormalities (eg, pseudo-Pelger-Hüet cells, ringed sideroblasts, dysplastic megakaryocytes) are not consistent with CR. In addition, ANC $> 1000/\mu\text{l}$ and platelet count of $\geq 100,000/\mu\text{l}$. Patient must be independent of transfusions. No duration requirement for this designation.

Cytogenetic complete remission (CCR) – Defined as morphologic complete remission plus a reversion to a normal karyotype. For this study, reversion of a normal karyotype is defined as no clonal abnormalities detected in a minimum of 20 mitotic cells.

Morphologic complete remission with incomplete blood count recovery (CRi) – Defined as morphologic complete recovery with the exception of neutropenia $< 1000/\mu\text{l}$ or thrombocytopenia $< 100,000/\mu\text{l}$.

Partial remission (PR) – Defined as meeting the above criteria for complete remission, with the following exceptions: decrease of $\geq 50\%$ in the percentage of blast to 5-25% in the bone marrow aspirate. A value of $\leq 5\%$ blasts in bone marrow with Auer rods present may also be considered a partial remission.

Stable Disease (SD) – Defined as not meeting the definitions of CR, CRi, PR, PD, or recurrence/morphologic relapse.

Progressive disease (PD) – Defined as a clear increase in bone marrow blast count, typically a greater than 50% increase compared with baseline, or new extramedullary disease. Patients with a $> 50\%$ increase in peripheral blast count with an increase of the total peripheral white blood cell count to $> 10,000/\mu\text{l}$ should undergo evaluation by bone marrow biopsy to access for progressive disease.

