9.2 Response Criteria - MDS

MDS Patients will be assessed for response according to the IWG criteria:⁶⁹

Complete remission (CR) – Defined as $\leq 5\%$ myeloblasts with normal maturation of all cell lines in the bone marrow and peripheral blood values of Hgb ≥ 11 g/dL, Platelets $\geq 100 \times 10^9/L$, Neutrophils $\geq 1.0 \times 10^9/L$, and 0% blasts. Persistent dysplasia does not exclude CR but will be noted.

Marrow Complete Response (Marrow CR) – Defined as $\leq 5\%$ myeloblasts in the bone marrow and a decrease by $\geq 50\%$ from pretreatment values, but not meeting the definition of CR above.

Partial Remission (PR) – Defined as meeting the definition of CR above with a decrease of myeloblasts in the bone marrow by $\geq 50\%$ from pretreatment values, but absolute myeloblasts still $>5\%$.

Stable Disease (SD) – Defined as not meeting the definitions of CR, Marrow CR, PR, SD, PD, or recurrence/morphologic relapse.

Progressive Disease//Relapse (PD) – Defined as $\geq 50\%$ increase in blasts to $> 5\%$ blasts (for patients with less than 5% blasts at baseline only), $\geq 50\%$ increase to $> 10\%$ blasts (for patients with 5-10% blasts at baseline only), $\geq 50\%$ increase to $> 20\%$ blasts (for patients with 10-20% blasts at baseline only), $\geq 50\%$ increase to $> 30\%$ blasts (for patients with 20-30% blasts at baseline only) or any of the following: At least 50% decrement from maximum remission/response in granulocytes or platelets, reduction in Hgb by ≥ 2 g/dL, or New or worsened transfusion dependence not related to study drug toxicity. Or for patients with a CR, Marrow CR, or PR as defined above and subsequently development of one of the following: Return to pretreatment bone marrow blast percentage, decrement of $\geq 50\%$ from maximum remission/response levels in granulocytes or platelets, or reduction in Hgb concentration by ≥ 1.5 g/dL or transfusion dependence.

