14.2.2 Primary Endpoint Analysis

The primary end-point of this phase II study is the correlation biomarkers with overall response in AML/MDS patients to decitabine.

We will correlate the presence of patient specific mutations (especially mutations in *DNMT3A*, *IDH1*, *IDH2*, and *TET2*) with overall response rates. Mutation rates in these genes and in other patient-specific genes will be correlated with overall response and their respective 95% confidence intervals will be provided.

Statistical considerations. The relationship between AML/MDS-associated mutations and the responsiveness to decitabine will be described by contingency tables and assessed using Chi-square test or Fisher's exact test as appropriate. The differentially expressed genes between responders and non-responders will be determined using the significance analysis of microarray (SAM). Multivariate logistic regression will also be fit to adjust the potential confounding effects of other demographic and clinical characteristics. The resultant critical *P* values will be corrected for multiple testing. Since the Bonferroni correction is known to be too conservative, a permutation analysis (e.g., 10,000 random assignments for

responsive status) will be used to derive an empirical critical P value. The new critical p-value is the number of permutation tests which yield a lower p-value than the original test divided by the total number of permutation tests.[61]

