A power analysis was performed using Chi-square test for the association between mutation and response to decitabine. The frequency of *DNMT3A*, *IDH1/2*, and *TET2* mutations in AML and MDS patients are each between 15% and 30% in multiple cohorts.[29-37] **Table 3** shows the minimal detectable differences of response rates between mutant and wild-type cases, assuming an expected overall 45% CR/CRi rate and 80% power. For an average of 20% frequency of a mutated gene, for example, 100 patients will provide 80% power to detect 30% difference at a 2-sided 0.1 alpha error. The purpose of this study is to determine whether any of these mutations result in a clinically significant association that would warrant pre-treatment testing. We believe that a reasonable cut off would be if at least 30% of clinical response could be attributed to the presence of a specific mutation. However, we anticipate that more power could be achieved as we assess patient groups with combined characteristics (e.g. *DNMT3A* mutation or loss of *DNMT3A* expression). In addition, we

Table 3. Detectable mutation associated response rates (80% power, $\alpha = 0.05$)

Total N	% of patients with a given mutation	Detectable response difference	Sensitivity of mutation to predict response at minimum detectable response difference*
100	15%	0.40	80%
	20%	0.35	75%
	30%	0.30	67%
	40%	0.27	61%
	50%	0.26	58%

* Assuming the overall response rate (CR/CRi) of 45%

expect that the majority of the enrolled 125 patients can be used in the analysis (since all of our molecular information will be acquired within 30 days of enrollment, we anticipate a drop-out rate of 20% or less).

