14.2.3 Secondary Endpoint Analyses

The overall response rate (CR/CRi/PR) and complete response rate (CR/CRi) will be compared with historical controls[2], and the 95% confidence intervals will be provided.

The rate of patient specific mutation clearance after 10, 28, and 56 days of therapy will be determined using an Illumina based platform. We will compare the rate of mutation clearance between the patients who achieve a CR/CRi after 4 cycles and those who do not. We anticipate that we will identify between 6 and 25 exonic SNVs per case (the range obtained with >200 AML samples sequenced to date with whole genome or exome sequencing), and that the expected 95% confidence

interval of the mean variant allele frequency will be $\pm 2.56\%$ and $\pm 1.25\%$, respectively, if we assume an anticipated standard deviation of 3.2% within the same clone. The change of tumor burden over time and its association with clinical response will be assessed using 2-way ANOVA for repeated measurement data, followed by the ad-hoc multiple comparisons for between-group differences (e.g., responders vs. non-responders) at given time points as well as the between-time differences within each group. The resultant critical P values will also be corrected using permutation analysis for multiple testing.

The steady-state plasma decitabine concentration on day 4 ± 1 will be measured and correlated with clinical overall response.

The percent decrease in bone marrow methylcytosine will be calculated on day 10 ± 1 . We will compare this reduction with previously published data and between the patients who achieve CR/CRi and those who do not. The correlation of peak plasma levels of decitabine with response will be assessed using 2-sample t-test or Mann-Whitney non-parametric rank-sum test as appropriate. The change of total bone marrow DNA methylcytosine from baseline and its association with both steady-state plasma drug levels and response will be assessed using 2-way ANOVA for repeated measurement data, followed by the ad-hoc multiple comparisons for between-group differences (e.g., responders vs. non-responders) and between-time differences. Similar analyses will be performed for the correlation of expression profiles and SNP analysis with pharmacokinetic data.

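### Overall response is never defined for MDS: CRi belongs to the AML criteria, and a Marrow CR fits no category in either listing of the endpoint.

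*Combined protocol and SAP*

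**What the plan says.** References are to the current protocol version, whose statistics are in Section 14.

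- **Primary endpoint (14.2.2):** "The primary end-point of this phase II study is the correlation biomarkers with overall response in AML/MDS patients to decitabine". The text does not say which response categories count.
- **First listing (14.2.3):** "The overall response rate (CR/CRi/PR) and complete response rate (CR/CRi"), in a sentence about comparison with historical controls. The same section splits patients by CR/CRi for the mutation-clearance and methylcytosine comparisons.
- **Second listing (Table 3 footnote, 14.2.2):** "Assuming the overall response rate (CR/CRi) of 45"%. The power text agrees with the footnote: "assuming an expected overall 45% CR/CRi rate and 80% power".
- **AML criteria (9.1):** "AML Patients will be assessed for response according to the IWG criteria". CRi appears here and only here: "Defined as morphologic complete recovery with the exception of neutropenia" or thrombocytopenia.
- **MDS criteria (9.2):** the categories are CR, "Marrow Complete Response (Marrow CR"), PR, SD and PD. There is no CRi.
- **Schedule changes (5.1 and 6.3):** AML CRi is paired with the point at which "MDS patients achieve a marrow complete response (Marrow CR) as defined in Section 9.0".
- **Analysis (14.2.2):** a chi-square or Fisher test on the pooled patients, multiplicity handled by randomly reassigning response status, and a logistic regression adjusting for demographic and clinical characteristics that are not listed.

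**The concern.** The endpoint uses a category that exists for one of the two diseases and leaves out the nearest category for the other. If the listings are applied as written, response is scored differently in AML and MDS, and the two are then pooled.

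Two things follow. Some MDS patients whose marrow has cleared move to the non-responder column, which dilutes any real mutation effect. And a gene that is more frequent in one disease picks up part of the scoring difference, because neither the primary test nor the permutation takes account of disease.

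If the listings are not applied as written, someone must decide how Marrow CR counts after the data are in hand, and that choice can move the primary p-value. The case will not be rare: MDS patients enter because of cytopenias (Section 3.1), so blast clearance without full count recovery is foreseeable.

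**Working it through.** **1. Where a Marrow CR falls.**

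| Category | Does an MDS Marrow CR qualify? | Reason |
|---|---|---|
| CR | No | 9.2 defines Marrow CR as not meeting CR |
| CRi | No | defined in 9.1 for AML only |
| PR | No | MDS PR needs blasts above 5%; Marrow CR needs 5% or less |

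Both listings therefore exclude it, and both include AML CRi. Under CR/CRi/PR, an MDS PR, with more residual blasts, counts while a Marrow CR does not. Haemoglobin adds to the asymmetry. MDS CR needs at least 11 g/dL, whereas AML CR sets no haemoglobin level and asks for transfusion independence. A transfusion-independent MDS patient with recovered neutrophils and platelets and haemoglobin of 10 g/dL can be at most a Marrow CR; an AML patient with the same counts who meets the other criteria is a CR.

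**2. The plan's own power.** Inputs from 14.2.2: 100 patients, 20% mutated (20 vs 80), overall rate 45%, difference 0.30, two-sided alpha 0.1.

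- Wild type: 0.45 − 0.20 × 0.30 = 0.39. Mutant: 0.39 + 0.30 = 0.69.
- Chi-square power is 79.3%, against 80% stated. It reproduces.

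For the 20% row of Table 3 (difference 0.35, alpha 0.05), wild type is 0.45 − 0.20 × 0.35 = 0.38 and mutant is 0.73. Power is 83% by exact enumeration of the chi-square test. This is the baseline for step 3.

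**3. Power under the literal reading.** Let m be the MDS share and q the share of MDS responses that are Marrow CR only. Neither is in the documents; I assume m = 20–40% and q = one third to one half. I also assume that response rates, the MDS share and q do not depend on mutation status. Observed rates are then the true rates times k = 1 − m·q, and 45·m·q responders per 100 patients change column.

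| m | q | k | Mutant / wild type | Responders recoded per 100 | Power |
|---|---|---|---|---|---|
| 0.20 | 1/3 | 0.933 | 0.681 / 0.355 | 3.0 | 77% |
| 0.20 | 1/2 | 0.900 | 0.657 / 0.342 | 4.5 | 74% |
| 0.40 | 1/3 | 0.867 | 0.633 / 0.329 | 6.0 | 71% |
| 0.40 | 1/2 | 0.800 | 0.584 / 0.304 | 9.0 | 65% |

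Wider assumptions (m = 10–50%, q = 20–60%) give 81% down to 56%.

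**4. False difference with no mutation effect.** Let everyone truly respond at 45%, let c be the proportion of MDS patients whose response is Marrow CR only, and let the gene frequency be fA in AML and fM in MDS.

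- MDS share among carriers: s1 = m·fM / [m·fM + (1−m)·fA].
- MDS share among non-carriers: s0 = m·(1−fM) / [m·(1−fM) + (1−m)·(1−fA)].
- Carrier minus non-carrier response: −c·(s1 − s0).

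Gene frequencies are the ends of the plan's 15–30% range. I assume m = 25% or 50% and c = 15 or 25 points.

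| fA, fM | m | s1, s0 | Difference, c = 15 | Difference, c = 25 |
|---|---|---|---|---|
| 15%, 30% | 25% | 0.400, 0.215 | −2.8 points | −4.6 points |
| 15%, 30% | 50% | 0.667, 0.452 | −3.2 points | −5.4 points |
| 30%, 15% | 25% | 0.143, 0.288 | +2.2 points | +3.6 points |
| 30%, 15% | 50% | 0.333, 0.548 | +3.2 points | +5.4 points |

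The size is about 2 to 5 points. It is zero if the gene is equally frequent in both diseases.

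**The case against.** The other side has five arguments.

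- **Status of the listing.** A reader might take CR/CRi/PR as the one stated definition of the primary endpoint. It is not. It stands in the secondary section, in a comparison with a historical study of older AML patients, where AML categories are natural, and the Table 3 footnote gives a different list. This stands, but the footnote omits Marrow CR too and adds a second conflict, over whether PR counts.
- **No coding rule.** A reader might infer that the plan codes Marrow CR as non-response. No section says so; that is the literal consequence of the listings. Section 5.2.9 speaks of clinical response as CRi or better for patients on 6-week cycles, which Section 6.3 also opens to MDS patients in Marrow CR, so CRi may be shorthand there for both diseases. This stands: the fault is an unspecified rule.
- **Not equivalent.** CRi and Marrow CR are paired only for schedule changes. CRi keeps the AML requirements of transfusion independence and no persisting pretreatment abnormalities; Marrow CR has neither, but adds a blast fall of at least 50%. Section 9.2 provides for baseline blasts below 5%, so a fall from 4% to 2% could qualify. This stands, and is why a sensitivity analysis is needed.
- **Regression.** The planned logistic model could adjust for diagnosis. It could then remove the confounding, but diagnosis is not named, and adjustment does not restore responders scored as failures.
- **Size.** Every magnitude is assumed. False differences of up to about 8 points need a gene frequency of 10% in one disease, outside the plan's 15–30%. Within that range, with the inputs of step 4, an uncorrected 5% chi-square test rejects about 5.5% to 8% of the time. This stands: the inflation is modest.

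**Conclusion.** The point holds as a gap in the primary endpoint. Neither listing of overall response has a place for an MDS Marrow CR, the two listings disagree about PR, and the pooled test and its permutation take no account of disease. It does not show that patients will be miscoded by a stated rule, or that AML CRi and MDS Marrow CR are the same state.

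Under the literal reading and the assumptions above, the main cost is power: 83% down to 77–65% in the 20% row of Table 3. The false association is secondary, at about 2–5 points within the plan's gene-frequency range. These figures are illustrative. That the category is unassigned follows from the text alone. It should be settled before the primary analysis, since a choice made afterwards could be steered by the results.

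**What to change.** 1. In Section 14.2.2, define overall response once, by disease: AML as CR, CRi or PR; MDS as CR, Marrow CR or PR.
2. Use that definition throughout 14.2.2, 14.2.3 and Table 3. State whether PR counts, and restate the power on the endpoint chosen.
3. Stratify the primary test by AML/MDS, permute response status within each disease, and name diagnosis as a covariate in the logistic regression.
4. Report a sensitivity analysis with Marrow CR coded as non-response.

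The cost is wording and a rerun of the power calculation. Marrow morphology and blood counts are already collected. The downside is that Marrow CR is a softer response, requiring neither transfusion independence nor the absence of pretreatment abnormalities; the sensitivity analysis shows how far the result depends on it.

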1.0 INTRODUCTION

1.1 Rationale

Personalized therapy for cancer requires that 1) patient-specific factors (e.g. patient-specific mutations, expression profiles, or pharmacogenomics) influence treatment algorithms, and 2) once therapy is initiated, *in vivo* responsiveness is used to guide further therapy. The modern era of genomics has provided significant insights into cancer pathogenesis by describing patterns of germline and somatic variants, as well as defining disease-specific patterns of gene expression. However, the application and integration of this data with therapeutics remains a difficult task.

Decitabine is a commonly used single-agent therapy for patients with acute myeloid leukemia (AML) and/or myelodysplastic syndrome (MDS). Historically, it has yielded clinical complete responses in approximately 25% of patients across diverse clinical trials, it is well tolerated, and it can be given as in the outpatient setting. However, the majority of patients do not respond to decitabine, the molecular etiology of decitabine sensitivity is unknown, and there are no algorithms to predict patient responsiveness *a priori* or even within one month of starting therapy.

AML and MDS are two closely related hematological disorders characterized by ineffective hematopoiesis and malignant expansion of clonal myeloid cells. Both AML and MDS frequently occur in elderly patients and some cases are secondary and/or related to long-term bone marrow damage after radiation or chemotherapy. Current therapy for AML consists of cytotoxic chemotherapy followed by consolidation chemotherapy or stem cell transplantation. Using these approaches, current cure rates may be as high as 60% for patients younger than 60 with good risk cytogenetics (e.g. t(15;17), t(8;21), inv(16)).[4] Outcomes in patients ≥ 60 years old and with relapsed disease remain poor with 2 year survival of only ~25%.[5] Historically, the available treatment for MDS has been symptomatic and has not been shown to be effective in producing sustained improvement in hematopoiesis or in delaying leukemic evolution[6, 7].

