1.2.2 Experience with extended dosing schedules

Blum *et al* recently published their experience treating elderly AML patients with a 10-day course of decitabine 20 mg/m²/day as a 1-hour infusion.[3] This

prolonged exposure course was designed to increase the number of AML blast divisions exposed to decitabine per cycle. Toxicities were very similar to a similar regiment given as a 3 and 5 day course,[2, 16] but the overall response (CR/PR) was much improved (64% vs 25%). In all three studies, the toxicities were primarily myeloid suppression and the resultant infectious and bleeding complications associated with leukemic and pharmacologic hematopoietic suppression. Furthermore, Blum *et al* noted that the percent methylcytosine reduction was improved (22% vs 11%) as was the time to blast clearance (50% of patients who ultimately achieved a CR had $\leq 5\%$ bone marrow blasts after 1 cycle vs 0% of patients after 2 cycles). Finally, like Shen *et al*, they observed a correlation between the extent of methylcytosine reduction and response.[28] This study suggests that improvement in response rates and time to response can be achieved by prolonged administration of decitabine. Further, that DNA methylcytosine reduction can be achieved with prolonged exposure to decitabine and that this might be a patient-specific biological marker of adequate dosing.

Scandura *et al*. recently published a study of infusional decitabine prior to cytarabine + daunorubicin induction therapy for AML.[64] They escalated the duration of infusional therapy and reached their planned goal of 20 mg/m²/day x 7 days of continuous therapy given prior to cytarabine and daunorubicin. They noted similar toxicities (primarily hematopoietic and the associated neutropenic infections), but that these were not different from their experience giving cytarabine + daunorubicin alone.

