
Genomic Predictors of Decitabine Response in AML/MDS

	
Treatment failure – Includes all patients who did not achieve a complete or partial remission.
 
Recurrence/morphologic relapse - Relapse following complete remission is defined as reappearance of blasts in the blood or the finding of $\geq 5\%$ blasts in the bone marrow, not attributable to any other cause. New dysplastic changes are considered a relapse. If there are no blasts in the peripheral blood and 5-20% blasts in the bone marrow, bone marrow biopsy should be repeated in > 1 week to confirm relapse.
 
Safety-- All patients receiving at least one dose of decitabine will be evaluated for safety.

Statistical considerations
	
This trial will be conducted as a phase II biomarker trial.
 
This trial is designed to detect the most clinically meaningful mutational predictors of response. These are mutations that have sufficient positive predictive value to be used as a clinical assay.
 
A power analysis was performed with Fisher’s exact test for mutation status and response to decitabine, assuming an expected 45% CR/CRi. With $\alpha = 0.05$, and a total anticipated enrollment of 100 evaluable patients, we anticipate 80% power to detect a 27% and 40% response difference between patients with and without a mutation, if the mutation occurs with a respective frequency of 30% and 15%. Such mutations would provide 80% sensitivity to predict response to decitabine. These are values that would warrant diagnostic clinical testing prior to therapy.
 
This trial is also designed to detect an improvement in clinical response compared to historical controls treated with 5 consecutive days of decitabine (20 mg/m²/day every 28 days)[2]. A power analysis was performed with Fisher’s exact test for response to decitabine compared to a historical rate of 24% observed in 55 patients. With 100 evaluable patients enrolled, we anticipate 90% power with $\alpha = 0.1$ to detect a 21% improvement in response (CR/ PR $\geq 45\%$). The reported CR/PR rate of the proposed treatment schedule (10 consecutive days of decitabine 20 mg/m²/day) is 64%[3]; the expected CR/PR rate of 45% is a conservative estimation of expected outcomes.

Study Schema:

Patients with progressive disease after two cycles (defined as a clear increase in bone marrow blast count, typically a > 50% increase in bone marrow blasts over baseline) should be removed from study.

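### Section 14.2.3 compares CRi-inclusive response rates with a 5-day benchmark that the documents record only alongside a CR/PR target, so like may not be compared with like

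*Combined protocol and SAP*

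**What the plan says.** The first-listed secondary objective (section 2.2) asks whether 10 days of decitabine per cycle gives better outcomes than 5 days did in historical controls. Section 14.2.3 is where this is analysed: "The overall response rate (CR/CRi/PR) and complete response rate (CR/CRi) will be compared with historical controls[2"], with 95% confidence intervals. It states no benchmark rate, test, alpha or sidedness for this comparison.

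Those details appear only in the Study Synopsis (Statistical considerations) of two earlier protocol versions in the same file. There, Fisher's exact test is used for response "compared to a historical rate of 24% observed in 55 patients", and with 100 evaluable patients "we anticipate 90% power with $\alpha = 0.1$ to detect a 21% improvement in response". The target carries the label CR/PR: "the expected CR/PR rate of 45% is a conservative estimation of expected outcomes". An earlier version of section 1.2.2 contrasts the 10-day schedule with 3- and 5-day courses in these terms: "but the overall response (CR/PR) was much improved (64% vs 25"%).

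The same 45% has a different label in the mutation power analysis of section 14.2.2: "assuming an expected overall 45% CR/CRi rate and 80% power".

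Section 9.1 (AML) requires neutrophil and platelet recovery for CR. It makes CRi a category of its own for patients who clear the marrow without that recovery. PR must meet the CR criteria apart from the blast requirement. Under these definitions a CRi patient is neither CR nor PR.

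**The concern.** A single-arm trial has no concurrent control, so a claim over history depends on both sides counting response the same way. Here both trial rates include CRi, while the one recorded benchmark is paired with a CR/PR target. If the 24% left CRi out, every CRi in the trial's CR/CRi/PR rate counts as a gain over a figure that could not include any. The 10-day schedule could then look better with an unchanged CR/PR rate, and this would happen even in an identical population.

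For CR/CRi the net effect is less certain. Relative to CR/PR it adds the CRi patients and drops the PR patients, so the shift is the CRi share minus the PR share.

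The mismatch does not arise only from reading one version against another. In the earlier versions, section 12.2.3 already compared CR/CRi/PR and CR/CRi with reference 2, while the synopsis of the same version powered CR/PR. The sentence was carried unchanged into 14.2.3.

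**Working it through.** **Inputs.** Historical 24% of 55; trial n = 100; target 45%; Fisher's exact test; alpha 0.1. All come from the earlier synopses, which do not state sidedness. The share of trial patients with CRi, x, is not in the documents and is assumed.

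**Method.** Let Y ~ Bin(55, p_H) be historical responders and X ~ Bin(100, p_T) trial responders. The pass probability is the sum of P(X)·P(Y) over all pairs where Fisher's p ≤ 0.1 in favour of the trial.

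**Step 1: reproduce the stated power.** With p_H = 0.24 and p_T = 0.45, power is 89.4% one-sided and 81.7% two-sided. The stated 90% is therefore a one-sided figure.

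**Step 2: count CRi in the trial only, with no true CR/PR gain.** Set p_H = 0.24 and p_T = 0.24 + x.

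| Assumed CRi, x | One-sided | Two-sided |
|---|---|---|
| 0 (matched definitions) | 7.5% | 3.8% |
| 2 points | 12% | 7% |
| 5 points | 23% | 14% |
| 10 points | 46% | 33% |
| 15 points | 70% | 57% |

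One-sided, the rate is 9.7% at 1 point and 11.0% at 1.5 points. Two-sided, it is just under 10% at 3.5 points and 11.2% at 4 points.

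**Step 3: hold the historical result fixed.** 24% of 55 is 13/55 (13 ÷ 55 = 23.6%). The smallest passing trial count is 35/100 one-sided (p = 0.099) and 38/100 two-sided (p = 0.076). The pass probability is P(X ≥ cut-off) with p_T = 0.24 + x.

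| x | One-sided, cut-off 35 | Two-sided, cut-off 38 |
|---|---|---|
| 0 | 0.9% | 0.1% |
| 2 points | 2.9% | 0.6% |
| 5 points | 11% | 3.3% |
| 10 points | 45% | 23% |

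**Step 4: match the definitions.** If 5 or 10 points of CRi are counted on both sides (29% versus 29%, 34% versus 34%), the one-sided false-positive rate is 7.9% in each case. Power for a 21-point gain is 87% and 86%.

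**Step 5: what the 90% power covers.** If the 45% already includes CRi and the historical rate with CRi is 29% or 34%, one-sided power is 71% or 46%. The 90% holds only for 24% versus 45% on one common definition.

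**The case against.** The strongest reply is that section 14.2.3 never sets 24% as the benchmark. It names two trial rates and one source study, and the natural reading is that each is compared with that study's own corresponding rate. The 24%, Fisher's test and alpha 0.1 belong to earlier synopses. This stands: a reader might infer that the current plan runs a 10% test with an inflated error rate, but the current section contains no such test. What remains is that it does not state which reference 2 numerators to use, and the only figure on record for that study is paired with CR/PR.

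Second, the 24% may already include CRi. The labels are used loosely, since the same 45% is CR/CRi in one place and CR/PR in another. The background figures do not settle it: the 25% in section 1.2.2 covers 3- and 5-day courses from two references, and the approximate 25% in section 1.1 is a complete-response figure across several trials. Parts of section 1.2 are redacted. This also stands. If CRi was counted, the problem is one of labelling and there is no inflation from this cause.

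Third, the historical result is already observed, so redrawing it at random overstates the effect of a small CRi share. With 13/55 fixed, the one-sided pass rate reaches only 11% at 5 points. That is fair for small shares; at 10 points the two calculations nearly agree (45% and 46%).

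Finally, this is a secondary comparison in a biomarker study, and no stopping rule in the documents depends on it. That limits the consequence but does not remove the mismatch.

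**Conclusion.** The response definitions do not match as written, and the current section leaves the benchmark unspecified. If the 24% excludes CRi, CR/CRi/PR is biased towards the 10-day schedule. With no true CR/PR gain, the one-sided pass rate would be about 23% at 5 points of CRi and 46% at 10, against 7.5% with matched definitions. It would be 14% and 33% two-sided, and 11% and 45% one-sided with history fixed at 13/55.

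These sizes rest on three assumptions: the earlier design is the one applied, the 24% contains no CRi, and CRi adds 5 to 10 points. The documents establish none of the last two and keep the first only in earlier synopses. A reader might conclude that the trial will exceed a 10% error rate by a wide margin; the documents do not support that. The supported conclusion is a possible bias, of unknown size, in the first-listed secondary objective, which can be removed cheaply. It should be corrected before the comparison is made.

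**What to change.** In section 14.2.3:

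- Compare each trial rate only with the rate from reference 2 that counts CRi the same way, and write in its numerator out of 55.
- If the 24% excludes CRi, test the trial's CR/PR rate against it with CRi counted as non-response.
- If the 24% includes CRi, relabel both the benchmark and the 45% target.
- Where reference 2 has no matching category, report the trial rate with its 95% confidence interval and claim no improvement.
- State the test, alpha and sidedness in the current text. If the 90% power is retained, say that it applies to 24% versus 45% on one common definition (one-sided alpha 0.1).

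The cost is wording plus one tabulation of response categories already collected. The downside is that the apparent gain over history may shrink and one of the comparisons may become descriptive.
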